9.1.1. Screen Failures

The number of screen failures and percent of screened subjects who are screen failures will be summarized along with reasons for screen failure on the disposition table. A listing of demographic information for screen failures will be provided.

9.2. Protocol Deviations

Protocol deviations will be identified and displayed in data listings by cohort, subject, study day, and (where applicable) date of deviation.

9.3. Demographic and Baseline Characteristics

Demographic data and baseline characteristics including age, sex, race, ethnicity, height, weight, body mass index (BMI), and HAE history will be summarized using descriptive statistics for the safety population, presented by cohort and overall. Age, height, weight, and BMI will be summarized as continuous variables. If not collected, baseline BMI will be calculated as:

$$\text{BMI} = \text{weight (kg)} / [\text{height (m)}^2].$$

Medical history will be coded using Medical Dictionary for Regulatory Activities (MedDRA) version 25.0. Demographic data, baseline characteristic data, and medical history will be listed by cohort, subject and medical history event diagnosis start date. Note that race/ethnicity is not collected from participants in France.

9.4. Listing of Subject Inclusion and Exclusion Criteria

Inclusion and exclusion criteria will be listed for each subject.

9.5. Prior and Concomitant Medications

Medications will be classified as prior or concomitant, coded using the World Health Organization Drug Dictionary (WHODrug Global B3 March 2022), and summarized by Anatomic Therapeutic Classification 4 term, preferred Term (PT), and cohort. Medications will be listed by cohort, subject, medication start date, medication stop date, and medication name.

9.6. HAE Medical and Medication History

HAE and HAE medication history will be summarized for the following where possible:

- HAE history
- Past on-demand treatments of HAE
- Current on-demand treatments of HAE
- Past prophylactic treatments of HAE

A summary of the HAE Medical History information as provided on the HAE Medical History page will be provided. A summary of screening complement 4 (C4), C1-INH antigen level, and functional C1 esterase inhibitor (C1-INHf) will be provided in categories showing how subjects met the inclusion criteria confirming diagnosis of HAE. Confirmation by SERPING1 gene mutation analysis, if required, will be included in the summary. Categories for C4 will be $C4 < \text{lower limit of normal (LLN)}$ and $C4 \geq \text{LLN}$ and for C1-INHf will be $< 50\%$, 50% to $< 74\%$, and $\geq 74\%$. Where the C4 test has been repeated, the test result for the repeat will be used in this summary.

Past prophylactic treatments will include those medications that were taken as prophylaxis and discontinued prior to the initiation of study treatment as recorded on the HAE Medication History Page. Past prophylactic medications will include Cinryze, Berinert, tranexamic acid, Takhzyro, HAEGARDA, and androgens. Androgens could include oxandrolone, danazol, and stanozolol.

Past on-demand treatments will include those medications that were taken as needed and discontinued prior to the initiation of study treatment as recorded on the HAE Medication History Page. Current on-demand medications will include those that are noted at screening as currently used for on-demand treatment as recorded on the HAE Medication History Page. Summaries of on-demand medications will include a grouping of any C1-INH medication as well as displays of individual medications. The C1-INH grouping will include plasma-derived C1-INH replacement (Firazyr, Cinryze on-demand, Berinert on-demand, Kalbitor) and recombinant C1-INH replacement (Ruconest). Fresh frozen plasma, a source of C1-INH, will also be considered an on-demand treatment and included with the plasma derived C1-INH replacements.

In addition, detailed SERPING data (laboratory confirmed or historically obtained) will be listed if provided.

9.7. Baseline Physical Examination

Physical examination findings, including baseline, will be listed.

9.8. Baseline Effectiveness Evaluations

All HAE attacks (subject-reported and adjusted) will be summarized on the corresponding effectiveness.

9.9. Exposure

The number and percentage of subjects exposed to berotralstat, and the duration of exposure (days) will be summarized by cohort. Individual dosing data will be listed by cohort, subject, and study day. Subjects who change doses over time will be noted.

Treatment adherence, dose interruptions, and reason for dose interruptions will be provided as summaries or listed as appropriate.

10. CLINICAL PHARMACOLOGY DATA ANALYSES

10.1. Pharmacokinetic Analyses

10.1.1. PK Concentrations

Analyses of concentration data will be performed using the PK population. All BCX7353 concentration data will be listed by subject, cohort, and time. The PK concentration data collected during the Week 2 visit will be summarized by cohort and overall, by nominal time. Concentration data from timed samples following dose modifications will also be summarized by cohort and overall, by nominal collection window. Concentration data from untimed samples will not be summarized as the nominal time of PK blood sample collection was not pre-specified; however, these concentrations will be included in the concentration listing.

For calculation of summary statistics for BCX7353 concentration data, concentrations that are below the limit of quantification (BLQ) will be treated as zero. Individual BLQ concentrations may alternatively be set to missing if deemed appropriate by the clinical pharmacologist (eg, BLQ result is implausible based on the totality of available data). If any values are set to missing for concentration analyses, this will be described in the CSR along with the rationale for doing so. These values will be reported as “BLQ” in individual-subject summaries (including listings) with a flag to denote the rationale for excluding in calculation of summary statistics.

If $\geq 33\%$ of the available concentration values at a given timepoint (or interval) are BLQ, only the number of samples, minimum, and maximum will be included in the summary tables. All other descriptive statistics parameters will be reported as “NC” (not calculable).

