10.9.1. Plasma Pharmacokinetic Samples for Dose Modifications

Adjustments to the berotralstat dose may be required during the study based on safety and/or PK findings. If the berotralstat dose is adjusted due to an AE or high exposure level, the subject will be required to provide blood samples for analysis of PK parameters as follows:

- Subjects in Cohorts 1 and 2 will provide a PK sample 20 to 24 hours after their previous dose of berotralstat, and another sample 2 to 4 hours after taking their daily dose of berotralstat.
- Subjects in Cohorts 3 and 4 will provide a PK sample 20 to 24 hours after their previous dose and, if possible, another sample at 2 to 4 hours after taking their daily dose of berotralstat.

These samples will be collected approximately 2 to 6 weeks after the dose adjustment. If a telephone call or telemedicine appointment is scheduled for the next visit, an in-person clinic visit may be conducted instead. Note: home health collection may be an option if available per country requirements.

Subjects with dose adjustment will be asked to take their daily dose in the morning for a minimum of 2 weeks before the PK draw will be completed. On the day of PK draw, subjects should take their daily dose during the visit with food.

The date and time of berotralstat dosing and PK sample collection, as well as whether the dose was taken with food, will be recorded in the source documents and the CRF.

Subjects with dose adjustments based on weight in Part 2 or Part 3 of the study should provide PK samples approximately 2 to 6 weeks after the dose adjustment, as described in the bulleted

list above. If samples cannot be collected in this timeframe, they must be collected at the next visit.

PK sample collection may be discontinued following the interim data cut used to finalize the population PK model and pharmacometric analysis report, at the discretion of the sponsor.

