7. TREATMENT COMPARISONS

7.1. Data Display Treatment and Other Sub-Group Descriptors

Planned groups to be displayed on the summary tables are based on the cohort corresponding to initial dose as determined by subject weight/weight band at study baseline:

Cohort	Dose	Weight Band (at baseline)
1	150 mg capsule	≥40 kg
2	108 mg granules	32 to <40 kg
3	96 mg granules	24 to <32 kg
4	78 mg granules	12 to <24 kg
All Cohorts	All Doses	12 to ≥40 kg

Unless otherwise noted, tables will be arranged by cohort, and listings will be sorted by cohort, subject number, and date. Subjects will be analyzed by their original assigned cohort. Subjects who have their dose changed (decreased or increased) may be footnoted in Tables and Figures (eg, 1 subject in Cohort 1 had a dose decrease to xxx mg in Part x or Week xx). In addition, a listing of subjects with dose increases or decreases will be generated.

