X	X*		14.1.5.1.2	Treatment Exposure and Compliance During Weeks 1-12	Week 12 Completer
X	X		14.1.5.1.3	Treatment Exposure and Compliance During Weeks 1-48	Week 48 Completer
X	X	X	14.1.5.2	Plot of Duration of Exposure to Study Drug	Safety
X			14.2.1.1.1	Summary of Plasma BCX7353 Concentrations (ng/mL) at Week 2	PK
X			14.2.1.1.2	Summary of Plasma BCX7353 Concentrations (ng/mL) Following Dose Modifications	PK
X			14.2.1.2.1	Summary of BCX7353 PK Parameters (New table to be specified by PK group)	PK
X	X		14.2.2.1.1	Summary of HAE Adjusted Attack Rate	Safety
X	X		14.2.2.1.2	Summary of HAE Adjusted Attacks Rate After Week 2	Safety
X	X		14.2.2.1.3	Summary of HAE Adjusted Attack Rate, During Weeks 1-12	Safety
X	X		14.2.2.1.4	Summary of HAE Adjusted Attack Rate, During Weeks 1-48	Safety

NDA IA	End of Part 2 (Wk 48) IA†	Final/ EOS**	Output Number	Title	Population
X	X		14.2.2.1.5	Summary of HAE Adjusted Attack Rate, During Weeks 1-12	Week 12 Completer
X	X		14.2.2.1.6	Summary of HAE Adjusted Attack Rate, During Weeks 1-48	Week 48 Completer
X			14.2.2.1.7	Summary of HAE Adjusted Attack Rate during the SOC Period	Safety
X			14.2.2.2.1	Summary of HAE Adjusted Attacks	Safety
X	X		14.2.3.2.1	Mean HAE Adjusted Attack Rate by Month	Safety
X	X*		14.2.3.2.2	Mean HAE Adjusted Attack Rate by Month, During Weeks 1-12	Week 12 Completer
X	X		14.2.3.2.3	Mean HAE Adjusted Attack Rate by Month, During Weeks 1-48	Week 48 Completer
X	X		14.2.3.3.1	Summary of Duration of Adjusted Attacks (hours)	Safety
X	X*		14.2.3.3.2	Summary of Duration of Adjusted Attacks (hours), During Weeks 1-12	Week 12 Completer
X	X		14.2.3.3.3	Summary of Duration of Adjusted Attacks (hours), During Weeks 1-48	Week 48 Completer
X			14.2.3.4.1	Summary of Attack Characteristics for Adjusted Attacks During the SOC Period	Safety
X	X		14.2.3.4.2	Summary of Attack Characteristics for Adjusted Attacks	Safety
X	X*		14.2.3.4.3	Summary of Attack Characteristics for Adjusted Attacks, During Weeks 1-12	Week 12 Completer
X	X		14.2.3.4.4	Summary of Attack Characteristics for Adjusted Attacks, During Weeks 1-48	Week 48 Completer
X			14.2.3.5.1	Summary of Attack Locations for Adjusted Attacks During the SOC Period	Safety
X	X		14.2.3.5.2	Summary of Attack Locations for Adjusted Attacks	Safety
X	X*		14.2.3.5.3	Summary of Attack Locations for Adjusted Attacks During Weeks 1-12	Week 12 Completer
X	X		14.2.3.5.4	Summary of Attack Locations for Adjusted Attacks During Weeks 1-48	Week 48 Completer

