X	X	X	14.3.5.3.2.3	Distribution Plots for PR Interval Observed Changes Relative to Baseline – All Observations	Safety
X	X	X	14.3.5.3.3.1	Plot of Mean (SD) QRS Observed Changes Relative to Baseline Over Time	Safety
X	X	X	14.3.5.3.3.2	Distribution plots for QRS Changes Relative to Baseline Over Time	Safety
X	X	X	14.3.5.3.3.3	Distribution plots for QRS Changes Relative to Baseline – All Observations	Safety
X			14.4.1.1	Acceptability/Palatability of the Berostralstat Oral Granules (limited to Cohort 2, 3, 4)	Safety

Listings:

NDA IA	End of Part 2 (Wk 48) IA	Final (Safety)	Listing Number	Title	Population
X	X	X	16.2.1.1	Informed Consent	All Subjects
X			16.2.1.2	Screen Failures	Screen Failures
X			16.2.2.1	Inclusion Criteria Not Met/Exclusion Criteria Met	ITT
X	X	X	16.2.2.2	Protocol Deviations	ITT
X	X	X	16.2.2.3	End of Study	ITT
X	X	X	16.2.3.1	Analysis Populations	ITT
X			16.2.3.2	Enrollment by Country and Site	ITT
X	X		16.2.4.1	Demographic and Baseline Characteristics	ITT
X			16.2.4.2	Confirmation of Clinical Diagnosis of HAE	All Subjects
X			16.2.4.3.1	Medical History	ITT
X			16.2.4.3.2	HAE Medical History – HAE Baseline Characteristics	ITT
X	X	X	16.2.4.3.3	HAE Medication History – Past and Current On-Demand HAE Treatment	ITT
X			16.2.4.3.4	HAE Medication History – Past Prophylactic HAE Treatment	ITT
X			16.2.4.4.1	Medications Taken within 30 Days of Screening and Discontinued Prior to Study Drug Initiation	ITT
X	X	X	16.2.4.4.2	Concomitant Medications	ITT
X	X	X	16.2.4.4.3	Use of Concomitant Medications for HAE	ITT
X	X	X	16.2.5.1	Drug Accountability and Compliance	ITT
X	X	X	16.2.5.2	Subjects with a Change in Dosing (All Doses)	Safety
	X		16.2.5.3	Plasma BCX7353 Pharmacokinetic Concentration Time Data	ITT
X	X		16.2.6.1.1	HAE Attack Diary Detail	ITT
X	X		16.2.6.1.2	HAE Attack Level Summary – Adjusted Attacks	ITT
X	X		16.2.6.1.3	HAE Attack Rate	ITT
X	X		16.2.6.2	Days with Angioedema Symptoms from Adjusted Attacks	ITT
X	X		16.2.6.3	Subject-Level Additional Derived Effectiveness Endpoint Profile	ITT
X		X	16.2.7.1.1	Adverse Events During the SOC Treatment Period	Safety
X		X	16.2.7.1.2	Serious Adverse Events During the SOC Treatment Period	Safety

X	X	X	16.2.7.2.1	Treatment-emergent Adverse Events	Safety
X	X	X	16.2.7.2.2	Serious Treatment-emergent Adverse Events	Safety
X	X	X	16.2.7.2.3	Related Serious Adverse Events	Safety
X	X	X	16.2.7.2.4	Treatment-emergent Adverse Events Related to Study Drug	Safety

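### Timed concentrations taken after a dose change are tabulated under the starting-dose cohort, and SAP Table 7 never schedules the PK tables and the concentration listing on the same cut

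*SAP*

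**What the plan says.** **Grouping.** SAP 10.1.1 gives the rule for samples taken after a dose change: "Concentration data from timed samples following dose modifications will also be summarized by cohort and overall, by nominal collection window". SAP 7.1 says what cohort means in the displays: groups are "based on the cohort corresponding to initial dose as determined by subject weight/weight band at study baseline". It adds: "Subjects will be analyzed by their original assigned cohort". Children whose dose changes "may be footnoted in Tables and Figures", and a separate listing names them.

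**Where the samples come from.** Protocol 10.9.1 requires PK samples after a dose change made for an adverse event or high exposure. It also extends the request to growth: "Subjects with dose adjustments based on weight in Part 2 or Part 3 of the study should provide PK samples". Protocol 8.4 says a modification may go up or down.

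**Schedule.** SAP Table 7 lists Table 14.2.1.1.2, "Summary of Plasma BCX7353 Concentrations (ng/mL) Following Dose Modifications", with a mark under the NDA interim only. The Week 2 concentration table (14.2.1.1.1) and the PK parameter table (14.2.1.2.1) are marked the same way. Listing 16.2.5.3, "Plasma BCX7353 Pharmacokinetic Concentration Time Data", is marked under End of Part 2 only. SAP 6.4 has concentrations both listed and summarised in the study report, and SAP 10.1.1 has all of them listed.

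**The concern.** In the Week 2 table the cohort is a fair stand-in for the dose, because children are still on what they were assigned on Day 1 unless something has already been changed. Table 14.2.1.1.2 is different: a sample enters it only because the dose was changed. A mean shown against a starting dose then describes a dose that nearly none of the contributing children was taking. If one child went up for weight and another came down for exposure, both fall in the same cell and the mean describes neither. SAP 10.1.2 allows a split by dosing regimen for the noncompartmental parameters, but 10.1.1 has no such provision for concentrations.

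The schedule is a second, separate gap. A reader of the NDA tables has no concentration listing from the same cut, and a reader of the End of Part 2 listing has no tables. Timed samples that arrive after the NDA cut are assigned to no table.

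**Working it through.** The plan is descriptive and gives no figure for this point. Its one sample-size figure does reproduce: 1 − 0.9^30 = 0.958, the roughly 96% in Protocol 12.1 and SAP 4.7. Nothing below uses it.

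**Inputs**
- Planned doses of 150, 108, 96 and 78 mg for Cohorts 1 to 4 (SAP 7.1, Protocol Table 1).
- Other strengths from 60 mg to below 150 mg may be used (note to Protocol Table 1).
- Weight-driven changes from Week 12 through Week 144, which is 132 weeks (Protocol Table 2 footnotes and synopsis).
- Table 7 marks as printed.

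**Step 1: label against actual dose.** Gap = actual dose / labelled dose − 1, for one-step moves between planned doses.

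| Label (mg) | Taking (mg) | Gap |
|---|---|---|
| 108 | 150 | +38.9% |
| 96 | 108 | +12.5% |
| 78 | 96 | +23.1% |
| 150 | 108 | −28.0% |
| 108 | 96 | −11.1% |
| 96 | 78 | −18.8% |

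A reduction to 60 mg, the lowest strength named, would give −60.0%, −44.4%, −37.5% and −23.1% from the 150, 108, 96 and 78 mg labels.

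**Step 2: opposite changes in one cell.** The documents give no counts, so this mix is assumed. Take a Cohort 2 cell of four samples, one at 150 mg and three at 96 mg. The mean dose is (150 + 3 × 96) / 4 = 109.5 mg, and 109.5/108 − 1 = +1.4%. The row looks right for the 108 mg label although no child in it took 108 mg. With all four at 150 mg the gap is +38.9%.

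**Step 3: the schedule.**

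| Output | NDA interim | End of Part 2 | Final |
|---|---|---|---|
| 14.2.1.1.1 | X | | |
| 14.2.1.1.2 | X | | |
| 14.2.1.2.1 | X | | |
| Listing 16.2.5.3 | | X | |

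No column holds both a PK table and the listing.

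**Step 4: what falls outside the tables.** SAP 10.1.1 does not summarise the untimed samples at any cut. The gap therefore concerns Week 2 profiles of children not yet sampled at the NDA cut, and timed post-change samples taken after it. For a child who has just reached Week 48 at the cut, 132 − 36 = 96 of the 132 weeks in which weight can change the dose are still ahead (96/132 = 73%). That is a share of time, not a forecast of samples.

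**The case against.** The strongest reply is that this table decides nothing. The weight-based dose comes from population PK modelling, which takes in the concentrations from the whole PK population (Protocol 12.2.4), has its own analysis plan and is reported separately (SAP 10.1.2). That stands. A reader might infer that mislabelled rows could distort the dose recommendation; the documents give no route by which they would.

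Other replies also have force:
- **Dose changes are traceable.** SAP 7.1 allows footnotes, SAP 9.9 lists individual dosing, and Listing 16.2.5.2 is marked for all three cuts. A reader could reconstruct the doses, but an optional footnote or a separate listing does not correct a mean. The shells are in another document and may add a dose label; the SAP does not require it.
- **Dose gaps are not exposure gaps.** Protocol 4.4.2 chose doses to match adult exposure in each weight group, so a child moved up for weight may show a smaller concentration gap than dose gap. After a change for high exposure or an adverse event, that matching cannot be assumed. The same argument gives the overall row some meaning, so dropping it would be preference.
- **The NDA cut is not limited to 15 children.** Fifteen Week 48 completers is the trigger. SAP 5.1 reports all available data, so any child past Week 2 can contribute. It is tempting to conclude that half the sample, or the lightest cohort, goes missing; the documents support neither. Cohort 4 has no noncompartmental analysis by design, so rerunning 14.2.1.2.1 would add no such results for it.
- **PK sampling may stop after the interim cut** (Protocol 10.9.1), and the final analysis covers disposition, dosing and safety (SAP 5.2). That may explain NDA-only tables. The stop is at the sponsor's discretion, however, so later samples remain possible.
- **The listing mark may be a slip.** 16.2.5.3 is the only listing without an NDA mark. It still needs correcting.

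**Conclusion.** The point holds at moderate weight: it should be fixed, but it does not threaten the primary endpoint.

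As written, Table 14.2.1.1.2 puts nearly all its samples under a dose not being taken, with one-step dose gaps of −28% to +39%, and it can average increases with reductions. The qualifier is nearly all because Protocol 11.2.2 lets an earlier dose be resumed, so a later sample could be back on the labelled dose. How often cells will mix directions is unknown, since the documents give no expected number of dose changes.

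The Table 7 marks conflict with SAP 6.4 and 10.1.1 for samples taken after the NDA cut. The number affected depends on enrolment at the cut and on whether the sponsor stops PK sampling. Because SAP 5.1 makes the NDA interim optional, no PK table is scheduled at all if it is not run.

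This concerns tabulation only and takes no view on any dose.

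**What to change.** 1. In SAP 10.1.1, summarise post-modification concentrations by the dose taken at sampling, within collection window. Keep the starting cohort as a secondary label, and show current weight and the reason for the change in the listing. Crossing dose with weight band and reason in the table itself would leave cells too thin to summarise, with about 30 children and cohort minimums of 3 or 4.
2. In Table 7, mark Listing 16.2.5.3 for the NDA interim as well, and mark the three PK tables for End of Part 2.
3. Run the tables and the listing at Final only if PK samples were collected after the earlier cut, and add a sentence to SAP 5.2 so that the final-analysis scope allows it.

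**Cost.** Some dose cells will be small; where only one or two values fall in a cell, the listing carries the information. The added work is three table runs and one listing run (3 + 1 = 4), and up to four more at Final if the condition is met. Table 14.2.1.1.2 needs a regrouped program, and 14.2.1.2.1 is still to be specified by the PK group, so these are not all simple reruns.

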10.1.2. PK Parameter Calculation

PK parameters will be calculated using noncompartmental and population PK methods.

Standard noncompartmental methods will be used to calculate the following individual subject PK parameters from observed plasma concentrations: C_{\max} , area under the concentration-time curve from time 0 to the last measurable concentration ($AUC_{0-\text{last}}$), area under the concentration-time curve from time 0 to 6 hours post-dose (AUC_{0-6}), time to C_{\max} (T_{\max}), last measurable concentration (C_{last}), and time to C_{last} (T_{last}) as data permit. Noncompartmental analyses will not be conducted for subjects in Cohort 4 due to the limited PK sampling in this group. Descriptive statistics will be calculated for each parameter and may be stratified by cohort and dosing regimen as appropriate.

Population PK modeling approach will be used to estimate the following PK parameters: AUC over the dosing interval (AUC_{tau}) at steady state, C_{\max} at steady state, T_{\max} , average plasma concentration (C_{avg}) at steady state, concentration at the end of a dosing interval (C_{trough}) at steady state, apparent clearance (CL/F), and apparent total volume of distribution (V_{ss}/F). Detailed methods for the population PK modeling approach can be found in the population PK analysis plan. The results of these analyses will be reported in the stand-alone pharmacometric report.

